**- Protocol Revision Record -**

Original Protocol:	January 27, 2015
Protocol Revision 1:	December 15, 2015
Protocol Revision 2:	January 12, 2016
Protocol Revision 3:	May 10, 2016
Protocol Revision 4:	July 12, 2016
Protocol Revision 5:	April 5, 2017

**PHASE I SCHEMA:**

**PHASE II SCHEMA:**

AR positive:  $\geq 10\%$  of tumor cell nuclei with immunoreactivity for AR in a CLIA certified laboratory

One cycle = 28 days, tumor assessment with scans will be performed after every 2 cycles

**STUDY CALENDAR: ENZALUTAMIDE +/- TASELISIB**

Evaluation a	Screening b Day-28 – Day 1	Daily	Treatment period								Every 2 cycles from CID1	Post treatment		
			Cycle 1 (28-days)		Cycle 2 (28-days) c			Additional cycles c	Cycle 4	End-of- treatment d		30 day follow-up d		
			Day 1	Day 15	Day 1	Day 8 t	Day 15	Day 1	Day 1					
Informed consent	X													
Inclusion/exclusion criteria	X													
Brain imaging (MRI or CT scan) e	X													
Demographics/ medical history	X													
Physical exam/signs & symptoms b,f	X		X	X	X	X	X	X	X			X		
Vital signs (including oxygen sat)	X		X	X	X	X	X	X	X			X		
12-lead ECG g	X													
ECOG Performance Status	X		X	X	X	X	X	X	X			X		
Blood collection	Clinical laboratory tests h	X		X	X	X	X	X	X			X		
	Fasting plasma glucose i	X		X	X	X	X		X			X		
	Pregnancy test j	X												
	HbA1C	X												
	PT (or INR)/PTT	X												
	PK assessments k					X		X		X				
	Circulating tumor DNA					X		X				X		
Tumor assessment CTs, bone scan l	X									X				
Archived tumor blocks/slides m	X													
Tumor biopsy (metastatic site) n	X						Day 14-21				X			
Imaging Correlate: CEST-MRI o	X						Day 14-21				X			
Enzalutamide administration (oral) p		X	Oral, once-daily administration											
Taselisib administration (oral): if on taselisib arm		X			Oral, once-daily administration, starting cycle 2, day 1									

Evaluation a	Screening b	Treatment period								Every 2 cycles from C1D1	Post treatment	
		Daily	Cycle 1 (28-days)		Cycle 2 (28-days) c			Additional cycles c	Cycle 4		End-of-treatment d	30 day follow-up d
	Day 1		Day 15	Day 1	Day 8 t	Day 15	Day 1	Day 1				
Pill Diary a		X										
Concomitant medications f	X		X	X	X	X	X	X				
Adverse events	X		X	X	X	X	X	X				X
Biopsy questionnaire g								X				

AE = adverse event; BSA = body surface area; CX = Cycle X, where X is the cycle number; DLT = dose-limiting toxicity; ECG = electrocardiogram; ECOG = Eastern Cooperative Oncology Group; HbA1C = glycosylated hemoglobin; IMP = investigational medicinal product; INR = international normalized ratio; PT = prothrombin time; PTT = partial prothrombin time; SAE = serious adverse event

- a Evaluation assessments should be performed prior to administration of IMP unless otherwise indicated. Results should be reviewed by the Investigator prior to the administration of the next dose. All visits should occur within 3 days of scheduled visit unless otherwise noted.
- b Screening must occur within 28 days of dosing. The following procedures must be repeated at the day 1 visit: Medical and cancer history, physical examination, weight measurement, vital signs, hematology (see h), serum chemistry panel (see h). Lab values must still meet eligibility criteria on cycle 1, day 1. Tumor assessments must be repeated at the baseline visit only if determined to be changed by clinical exam or other clinical observations. SOC procedures performed prior to consent but within the protocol defined screening window for each assessment can be used for study purposes. All research only procedures must be performed after the consent date.
- c Patients may continue with daily dosing of enzalutamide with or without taselisib in the absence of unacceptable toxicities after C2 (or if the toxicity has resolved) and with no clinical evidence of disease progression.
- d The 30-day follow-up assessments should be done 30 (±3 days) days after the last dose of enzalutamide and taselisib. 30 day follow-up can be done by phone or by a clinic visit. Any ongoing toxicities should be documented. Any ongoing serious adverse events will be followed every 3 months until resolution. Any AEs or SAEs considered possibly or probably related to IMP that have not stabilized, returned to baseline, or are considered irreversible will continue to be monitored as per the protocol in Section 7.
- e MRI should be completed only if CT is unclear and a lesion can only be followed on MRI imaging. The CT scan should be completed with contrast. This is considered a research procedure if the patient does not have any signs or symptoms of brain metastases. If the patient must undergo brain imaging for the sole purpose of screening for this study, it is expected that a CT of the head will be done.
- f The physical examination will include measurements of height and weight at screening. Weight will be measured on day 1 of each cycle and at the End-of-treatment visit. Physical examination will include examination of major body systems including neurologic, cardiac, respiratory, gastrointestinal, and skin. Clinically relevant signs and symptoms will be reported as AEs.
- g ECG will be performed at screening
- h Clinical laboratory tests will include hematology and serum chemistry panel including white blood cell count, differential, hemoglobin, platelet count, sodium, potassium, chloride, bicarbonate, BUN, creatinine, glucose, calcium, and magnesium, SGOT, SGPT, and total serum bilirubin, albumin, and total protein. Additional tests will be performed when clinically appropriate. In case of Grade 3 or higher abnormal liver function results, additional testing will be done weekly until recovery to baseline value (see section 7.2). For all other timepoints, labs can be performed up to 3 days prior to each timepoint indicated in the study calendar (other than required C1D1 timepoint). Results from labs obtained on C1D1 do have to meet eligibility criteria.
- i FPG (fasting plasma glucose) will be collected at screening, on Days 1 and 15 of C1, on CXD1 of subsequent cycles, and at the End-of-treatment visit. FPG will also be monitored if patients experience Grade ≥1 hyperglycemia during the course of the study per the hyperglycemia management guidelines provided in the protocol. FPG can be obtained up to 3 days prior to each timepoint indicated in the study calendar (other than required C1D1 timepoint). Fasting plasma glucose is the same as serum glucose on days that the patient is fasting. On days the patient is getting non-fasting labs, it should be serum glucose only. (See Table 3 under section 7.2.1.5)
- j Serum pregnancy test: women of child bearing potential must have a negative serum pregnancy test result within 28 days prior to the initial dose of IMP.

- k PKs for patients in the phase Ib portion: plasma sample should be obtained on Cycle 1, day 8 at: 0-4 hours prior to dose of taselisib and 1, 3, and 6 hours post administration taselisib. On Cycle 2, day 15 at: 0-4 hours prior to dose of taselisib and enzalutamide and 1, 3, and 6 hours post administration taselisib and enzalutamide. On Cycle 4, day 1, plasma sample should be obtained 0-4 hours before taselisib and enzalutamide administration, and 3 hours post-administration of both drugs. PKs in phase II will occur for 10 patients at the Vanderbilt site only and should be obtained on patients receiving both enzalutamide and taselisib: C2D1, C2D15, and C4D1 at 0-4 hours prior to taselisib and enzalutamide and 2 to 4 hours post treatment.
- l Tumor assessment should be performed approximately every 2 cycles (up to -5 days) while on study treatment and at End-of-treatment visit if not obtained within the past 6 weeks. Scans should consist of CT scan of the chest, abdomen, and pelvis and a bone scan at baseline. Subsequent scans should consist of CT chest, abdomen and pelvis, and bone scan if bone metastases were present on the baseline studies. At the end of treatment, all scans (baseline and through disease progression) should be sent on a CD to the Vanderbilt Cancer Imaging Support Laboratory for central review and assessment. See Section 10.5 for details and address.
- m Archived tumor biopsy specimen: 20 unstained slides of archived biopsy block (unstained slides) or fresh tumor biopsy will be requested at the time of enrollment prior to initiation of treatment.
- n Tumor biopsies will only be performed in the phase II portion. A tumor biopsy from a metastatic site will be obtained from patients prior to day 1, at cycle 2 day 14-21, and upon progression of disease. The third biopsy (at the end of treatment) will not be required for patients who are removed from study for reasons other than disease progression. A patient who undergoes a research biopsy procedure for the purpose of this protocol, and in whom inadequate tissue is obtained, is not obligated to undergo a repeat biopsy.
- o See section 9.1. Required only for patients at Vanderbilt and only in the phase II portion. This should be performed prior to tumor biopsy, if possible. If MRI sub-study is not feasible due to scheduling, MRI weight limits, etc., patients may still continue with the remainder of the study.
- p Subjects on the enzalutamide + taselisib arm should begin enzalutamide on day 1 of cycle 1, and taselisib on day 1 of cycle 2.
- q Pill Diary can be found in the packet of supplemental forms.
- r See Section 6.4.2.
- s Phase II only. Biopsy questionnaire should be filled out by the patient on C3D1. Form can be found in the packet of supplemental forms.
- t The cycle 2 day 8 visit is only needed for patients on the combination of taselisib + enzalutamide. Patients on enzalutamide only do not need a visit on this day.

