- 4.1.11** Phase II only: Biopsy of a metastatic lesion in patients with reasonably accessible metastatic lesions (chest wall, skin, subcutaneous tissue, lymph nodes, skin, breast, bones, lung, and liver metastases). If a reasonably accessible metastatic lesion is not available, the patient may go on study provided that archived tissue is available. However, if a reasonably accessible site is available for biopsy, the patient must agree to biopsy. Any patients not undergoing biopsy must be approved for study enrollment by the Protocol Chair. Biopsies may be done with local anesthesia or intravenous conscious sedation, according to institutional guidelines. If a biopsy requires general anesthesia, then it is only allowed if acquisition of tissue is clinically indicated, and excess tissue may be collected for research purposes. Patients without sites available for biopsy must have available tissue [archived formalin-fixed paraffin embedded blocks (FFPB) or fresh frozen tissue from original diagnosis or metastatic setting] for correlative studies per Section 9.2.

Tissue needs to be located and available at the time of registration (tissue needs to be submitted within 3 weeks of study initiation).

**4.1.12** Patients must have adequate hematologic, hepatic, and renal function. All tests must be obtained within 28 days of starting treatment. Labs are to be repeated on C1D1 and must still meet eligibility. These include:

- ANC  $\geq 1500/\text{mm}^3$
- Platelet count  $\geq 75,000/\text{mm}^3$
- HgB  $\geq 9$  g/dL
- Creatinine  $\leq 1.5X$  upper limits of normal (ULN)
- INR  $\leq 2$
- Total serum bilirubin  $\leq 1.5$  x ULN (in patients with known Gilbert Syndrome, a total bilirubin  $\leq 3.0$  x ULN, with direct bilirubin  $\leq 1.5$  x ULN)
- AST and ALT  $\leq 3$  x ULN (or  $\leq 5.0$  x ULN if hepatic metastases are present)
- For patients without known Type II diabetes, the following is required at screening:
  - Fasting plasma glucose  $\leq 160$  mg/dL (7.49 mmol/L) and glycosylated hemoglobin (HbA1c)  $< 7.5$  % or International Federation of Clinical Chemistry (IFCC)  $< 53$  mmol/mol
- For patients with Type II diabetes receiving only oral anti-hyperglycemic therapy (patients receiving insulin are not eligible), the following are required at screening:
  - HbA1c  $< 8.5$  % or IFCC  $< 69.4$  mmol/mol
  - Stable regimen of oral anti-hyperglycemic therapy without insulin usage for at least 3 weeks prior to first study treatment

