  - Fasting plasma glucose levels  $\leq 160$  mg/dL (8.88 mmol/L) and no hypoglycemia (BS  $< 60$ ) during home monitoring for at least 1 week prior to study entry

**4.1.13** Patients must be able to swallow and retain oral medication.

**4.1.14** For patients who are not postmenopausal or surgically sterile (absence of ovaries and/or uterus), agreement to remain abstinent or to use two adequate methods of contraception (e.g., condoms, diaphragm, vasectomy/vasectomized partner, tubal ligation), during the treatment period and for at least 30 days after the last dose of study treatment or 3 months after discontinuation of taselisib and/or enzalutamide, whichever is longer. Hormone based oral contraceptives are not allowed on study. Postmenopausal is defined as:

- Age  $\geq 60$  years
- Age  $\leq 60$  years and amenorrheic for 12 months in the absence of chemotherapy, tamoxifen, toremifene, or ovarian suppression; or follicle stimulating hormone and estradiol in the postmenopausal range

**4.1.15** Patients may have received radiation therapy to painful bone metastases or areas of impending bone fracture as long as radiation therapy is completed  $\geq 2$  weeks prior to day 1 of cycle 1 of treatment. Patients who have received prior radiotherapy must have recovered from toxicity ( $\leq$  grade 2) induced by this treatment. Baseline radiologic scans must be obtained after completion of radiation.

**4.1.16** Patients must complete all screening assessments as outlined in the protocol.

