### 6.3.1 Taselisib

Taselisib tablets are administered once daily until disease progression or intolerable toxicity. Taselisib administration will begin on C2D1 for patients enrolled on the combination arm (with enzalutamide alone beginning on C1D1). Each dose should be taken with a minimum of 3–4 ounces (90–120 mL) of water with or without food in the morning (before noon). If a dose is missed (not taken by noon), the patient will resume dosing with the next scheduled dose. Missed or vomited doses will not be made up. The occurrence and frequency of any vomiting during a treatment cycle must be noted as an adverse event. Patients should swallow the capsules as a whole and not chew or crush them.

A sufficient number of taselisib tablets should be provided to the patient to last until the next cycle. Patients will be instructed to bring their bottles of study drug and their medication diary with them to each study visit.

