#### 7.2.1.3 *Dermatological Toxicity*

Treatment-related rash, including cases of Grade 3 rash, has occurred in patients who received taselisib. This rash is commonly manifested as maculo-papular with or without pruritus. Incidence rate and severity of rash appear to be dose dependent. The rash has resolved upon holding of taselisib and/or supportive therapy (e.g., topical or systemic steroids). Rash and other dermatological events should be closely monitored, and patients with severe rash should be monitored for associated signs and symptoms such as fever and hypotension that may be suggestive of a systemic hypersensitivity reaction. For severe rash, dosing of taselisib should be interrupted, and patients should be treated with supportive therapy per standard of care. Use of topical antihistamine, as well as topical or systemic corticosteroids, may be considered. Dose delay and modification guidelines for patients who experience rash are outlined in Table 3. Of note, no grade 3 or 4 rashes were noted in the phase Ib portion of this study with dose escalation to 8 mg taselisib. However, in the phase II portion with taselisib at 4 mg, 7 of 8 patients on the combination arm experienced a grade 3 or 4 rash with fever within the first 14 days of treatment. No patients who crossed over from enzalutamide to taselisib + enzalutamide experienced the rash, thus the study is amended so that all patients have a 28 day lead-in with enzalutamide prior to starting taselisib (similar to the cross-over arm). The rash resolved in all patients with IV steroids, antihistamines and supportive care.

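### The eligibility lab check stayed at C1D1 when the combination arm's first taselisib dose moved to C2D1, so no stated glucose limit applies to that first dose (minor)

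*Combined protocol and SAP*

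**What the plan says.** The lab requirement appears in three places, each tied to C1D1:

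- Main study calendar, footnote b: "Lab values must still meet eligibility criteria on cycle 1, day 1".
- Main study calendar, footnote h: "Results from labs obtained on C1D1 do have to meet eligibility criteria".
- Inclusion criterion 4.1.12: "Labs are to be repeated on C1D1 and must still meet eligibility".

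The fasting plasma glucose (FPG) limit in 4.1.12 is 160 mg/dL for patients with and without Type II diabetes. The mmol/L equivalents differ: "mg/dL (7.49 mmol/L) and glycosylated hemoglobin (HbA1c" for patients without diabetes, and "mg/dL (8.88 mmol/L) and no hypoglycemia" for those with it.

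On the start of taselisib, 6.3.1 says: "Taselisib administration will begin on C2D1 for patients enrolled on the combination arm". Section 7.2.1.3 gives the reason. After severe rash in the combination arm, the study was amended so that "all patients have a 28 day lead-in with enzalutamide prior to starting taselisib (similar to the cross-over arm").

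For crossover patients, 6.6 requires the inclusion values to be met before taselisib, on assessments no more than 28 days before Day 1 of Cycle 1X.

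On glucose during treatment, footnote i schedules FPG on C1D1, C1D15 and Day 1 of each later cycle, and adds: "FPG will also be monitored if patients experience Grade ≥1 hyperglycemia during the course of the study per the hyperglycemia management guidelines".

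**The concern.** The glucose limit at entry chiefly protects the taselisib dose. Hyperglycemia is a documented taselisib effect (3.3.1.1, 7.2.1.1), while the common enzalutamide reactions listed in 7.3 do not include it. When taselisib started on C1D1, a C1D1 lab check stood directly before it. The amendment moved the first dose by 28 days and left the check where it was, so it now stands before a cycle of enzalutamide alone.

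The amendment took the crossover sequence as its model but did not bring over the rule in 6.6 that ties stated values to the start of taselisib. A combination patient with an FPG of, say, 200 mg/dL on C2D1 could start taselisib, although 4.1.12 would not have admitted that patient on C1D1.

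For background, taselisib-related Grade 3–4 hyperglycemia was 12% with the single agent (3–16 mg in escalation, 9 mg in expansion), 4% with letrozole and 15% with fulvestrant (both 6–9 mg). The phase II dose is 4 mg, so the rate here may be lower.

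**Working it through.** There is no stated figure to reproduce. The check sets the rules side by side and measures the gap.

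**1. Which rule covers the first taselisib dose?**

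| Source | What it requires | Limit before a first dose on C2D1? |
|---|---|---|
| Footnotes b, h; 4.1.12 | Labs meet eligibility on C1D1 | No, wrong day |
| Footnote a | Investigator reviews results before the next dose | No value given |
| Footnote i | FPG drawn on C2D1, up to 3 days early; extra monitoring if hyperglycemia occurs | No value given |
| Table 3, Grades 1 and 2 | Dose level maintained; at Grade 2 also re-check and treat, with hold or continue left to the investigator | No required hold |
| Table 3, Grade 3 and above | Hold until Grade 2 or lower | Yes, by extension (see below) |
| 6.6 | Inclusion values met before taselisib | Crossover patients only |

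Table 3 is titled for taselisib-related toxicities, so even its Grade 3 hold reaches a patient not yet on taselisib only by extension. Taking 250 mg/dL as the upper edge of the gap is therefore the cautious choice.

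**2. Width of the gap.** The lower edge is 160 mg/dL (4.1.12). The upper edge is 250 mg/dL, where Grade 3 begins (Table 1). Width: 250 − 160 = 90 mg/dL. The documents do not print the Grade 1 and Grade 2 ranges, but neither grade requires a hold, so the band does not depend on where they divide.

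**3. Units.** From the protocol's own pairs, 160 / 8.88 = 18.02 mg/dL per mmol/L, and 250 / 13.9 = 17.99. Then 7.49 × 18.02 = 135 mg/dL. The figure printed for patients without diabetes therefore does not equal 160 mg/dL. Read literally, it would widen the band to 250 − 135 = 115 mg/dL.

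**4. Age of the qualifying labs at C2D1.** Nominally 28 days, or 25 to 31 with the 3-day visit window.

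**5. Cost of a delay.** Week 16 is day 112. Planned taselisib exposure by then is 112 − 28 = 84 days. A one-week delay leaves 84 − 7 = 77 days, a loss of 7 / 84 = 8%.

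**The case against.** The strongest reply is that the band is already managed and only a fixed number is missing. FPG is drawn on C2D1 and the result must be reviewed before dosing. Footnote i applies the hyperglycemia guidance throughout the study, and at Grade 2 the investigator may hold. FPG is also drawn on C1D15 and, as far as the calendar layout can be read, on C2D8. This stands, and it is why the point is minor. But these are rules for review or for continuing treatment; none is a criterion for a first dose.

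Table 3 also lets taselisib resume after a Grade 3 event once glucose is at Grade 2 or lower, so a start limit of 160 mg/dL would be stricter than the restart rule. That is a fair argument about which limit to choose, not for having none.

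Some of the 4.1.12 glucose wording refers to screening or study entry, so applying the limit on C1D1 is partly inference. It rests on the general C1D1 sentence in 4.1.12 and on footnote i calling the C1D1 timepoint required. If the limit applied at screening only, the qualifying value could be 28 + 28 = 56 days old at C2D1, which makes the gap larger.

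A reader might infer more than the documents support:

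- *That crossover patients face a fresh check and combination patients a stale one.* Section 6.6 accepts assessments up to 28 days old, much the same age as C1D1 labs at C2D1. The crossover calendar draws labs on Day 1 or up to 7 days before, but 6.6 does not say the latest value decides. The real difference is that 6.6 ties stated values to the taselisib start.
- *That ANC, platelets and creatinine need the same start limit.* They have no stated C2D1 value either, but the documents show no comparable gap for them.
- *That the 12%, 4% and 15% rates measure the risk here.* They do not describe patients starting taselisib in this glucose band, nor the 4 mg dose.

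**Conclusion.** The point holds as a minor safety alignment. In the combination arm, an FPG above 160 and below 250 mg/dL on C2D1 meets no stated bar to the first taselisib dose, and the decision is left to the investigator. The number of patients affected cannot be estimated from the documents. It is probably small, because the enzalutamide reactions in 7.3 do not include hyperglycemia. The two-stage design, its error rates and the sample size are untouched.

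This rests on two readings. The 160 mg/dL limit is taken to apply on C1D1 and not only at screening. The C2D1 start in 6.3.1, 7.2.1.3 and footnote p is taken to govern; 9.5 still describes a Day 1 taselisib start for the first ten combination patients at the coordinating site. For anyone treated that way, the C1D1 check would coincide with the first taselisib dose and the gap would not arise.

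**What to change.** - In 6.3.1 and footnotes b and i, require the already scheduled C2D1 FPG (drawn up to 3 days earlier) to be at most 160 mg/dL before the first taselisib dose. If the team prefers a looser limit, it should write that limit down.
- If the value is higher, continue enzalutamide, start or intensify anti-hyperglycemic treatment, re-check, and begin taselisib once the limit is met.
- State that missing the limit delays or omits taselisib but does not remove the patient from the study or from the CBR analysis. This matters because 7.2 discontinues patients from the study after a dose delay of more than 28 days. Applied to a first dose, that rule could remove a randomized patient for a modestly raised glucose. Section 15.7 already keeps patients with a changed schedule in the CBR analysis.
- In 4.1.12, correct 7.49 mmol/L to 8.88 mmol/L.
- Do not add ANC, platelet or creatinine limits at C2D1.

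The cost is a few sentences and no new test. The downside is a short taselisib delay in a few patients, with the loss of exposure shown above for one week.
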